3.1 Inclusion Criteria

- Healthy volunteer
- Age 18 – 65 years
- Hemoglobin A1c < 6.0%

CONFIDENTIAL

3.2 Exclusion Criteria

- History of diabetes, hyperglycemia, stroke, seizures, arrhythmias, active cardiac disease
- Pregnancy or plan to become pregnant during the study period
- Diagnosis of asthma (increases risk of hypersensitivity reactions to NAC)
- Use of anti-oxidants or drugs that can alter glucose metabolism
- Concomitant medical problems that may prevent the subject from successfully completing the protocol
- Unwillingness to avoid exercise during the 7 days before each part of the study

3.3 Subject Recruitment and Screening

Subjects will be recruited from a registry of normal volunteers who are interested in participating in research that is maintained by the investigator. In addition, subjects will be drawn from the community using IRB approved public notices. The only laboratory testing necessary to meet inclusion/exclusion criteria will be a hemoglobin A1c done in the last month.

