2.1 General Design

This is a single center, double blind randomized cross over design trial that will compare the impact of NAC vs. saline infusion during experimental hypoglycemia on day one on the responses to experimental hypoglycemia on day two. Figure 1 shows the protocol in schematic form. We intend to enroll 18 individuals to obtain the complete data sets from 15 participants.

Expected duration of subject participation is 10-12 weeks. This study will consist of a screening visit and two 2-day intervention visits separated by approximately 8 weeks.

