3.4 Early Withdrawal of Subjects

3.4.1 When and How to Withdraw Subjects

Subjects will be withdrawn at any point during the study if they remove their consent or if they develop any of the exclusion criteria after enrollment. In addition, any subjects who experience the symptoms of an allergic reaction to the NAC severe enough that the infusion is stopped early will be withdrawn from the study at the time the infusion is stopped (before unblinding that participant's treatment assignment). Procedures for withdrawal include collecting the necessary information to provide them with the compensation due them for the time they devoted to the study. At the end of the study, after treatment assignments are unblinded, a letter will be sent to the any subject withdrawn because of symptoms of an allergic reaction to NAC informing them of the treatment they were given. If they had been given NAC, we will instruct them to share the letter with their personal physician so the allergy could be noted in the clinical record.

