4.8.4 Return or Destruction of Study Drug

At the completion of the study, there will be a final reconciliation of drug shipped, drug consumed, and drug remaining. This reconciliation will be logged on the drug reconciliation form, signed and dated. Any discrepancies noted will be investigated, resolved, and documented prior to return or destruction of unused study drug. Drug destroyed on site will be documented in the study files.

5 Study Procedures

This study will consist of a screening visit and two 3-day intervention visits separated by approximately 8 weeks.

At the screening visit (approximately 2-4 days prior to study day one) informed consent will be obtained, the clinical history will be reviewed to be certain a volunteer meets the inclusion criteria and baseline hemoglobin A1c will be obtained.

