cysteine, glutathione, and GSH/GSSG ratios. After the completion of the afternoon clamps, subjects will be returned to euglycemia and fed a meal. They will then be allowed to leave the research center with instructions to return the next morning. At 7 AM on day 2 they will undergo a single 2 hour hyperinsulinemic hypoglycemic stepped clamp (75, 65, 55, 45 mg/dl targets) during which blood samples will be collected as on the morning of day 1. Symptom scores will be collected in the final 15 minutes of each step in the clamp. At the end of the study, infusions will be stopped, they will be fed and meal and then be sent home after they are scheduled to return for Part 2 in 8 weeks. This timing is selected to ensure that female participants are studied at the same phase of the menstrual cycle; males will return for Part 2 in 8±2 weeks. During Part 2 they will receive the treatment not provided during Part 1 in a blinded fashion. The rest of the study protocol will be the same as in Part 1.

A description of the study visits is below:

Visit description	Expected activities
Screening	
 • Confirm subject qualification • Obtain informed consent • Baseline A1c
Part 1 Day 1	
 • Randomization • Morning (8 – 10 AM) hyperinsulinemic hypoglycemic clamp study with infusion of NAC or saline depending on randomization assignment, collection of counterregulatory hormones and hypoglycemia symptom scores • Afternoon (1 – 3 PM) hyperinsulinemic hypoglycemic clamp study with infusion of NAC or saline depending on randomization assignment
Part 1 Day 2	
 • Hyperinsulinemic stepped hypoglycemic clamp study with collection of counterregulatory hormones and hypoglycemia symptom scores • Lunch
8 week wash out period	Usual activities
Part 2 Day 1	
 • Morning (8 – 10 AM) hyperinsulinemic hypoglycemic clamp study with infusion of NAC or saline depending on randomization assignment, collection of counterregulatory hormones and hypoglycemia symptom scores • Afternoon (1 – 3 PM) hyperinsulinemic hypoglycemic clamp study with infusion of NAC or saline depending on randomization assignment
Part 2 Day 2	Hyperinsulinemic hypoglycemic clamp study with collection of counterregulatory hormones and hypoglycemia symptom scores 
 • Lunch

CONFIDENTIAL

6 Statistical Plan

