6.3 Subject Population(s) for Analysis

In this version of the protocol, we intend to only study healthy volunteers. In the original version, we intended to enroll humans with type 1 diabetes of less than 20 years duration, with A1c 6.9-8.2%, who were aware of hypoglycemia but were unable to reach our recruitment goals with this population. More than 45 potential participants were contacted over 14 months and only one subject was able to complete the entire protocol. The reasons potential participants refused enrollment included strong preferences to not experience hypoglycemia and inability to commit the time necessary to complete the study. Previously our group has had no trouble enrolling enough normal volunteers to participate in studies in which they were asked to experience several periods of hypoglycemia. Thus, we believe that we will meet our recruitment goals by changing the population to normal volunteers. In addition, this is a proof of principle study in which the impact of NAC on hypoglycemia induced blunting of the counterregulatory response will be measured. Normal volunteers who participate in this protocol are expected to have the same degree of hypoglycemia induced blunting in their counterregulatory response as patients with type 1 diabetes and normal awareness of hypoglycemia. Therefore, this redesign will allow us to determine if NAC works under controlled conditions. If it does, it will provide rationale to use in in patient populations in the future.

Exclusion criteria will include history of diabetes, hyperglycemia, stroke, seizures, arrhythmias, active cardiac disease, pregnancy or plan to become pregnant during the study period; diagnosis of asthma (increases risk of hypersensitivity reactions to NAC); use of anti-oxidants or drugs that can alter glucose metabolism; concomitant medical problems that may prevent the subject from successfully completing the protocol; and an unwillingness to avoid exercise during the 7 days before each part of the study.

7 Safety and Adverse Events

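### Pregnancy is an exclusion and a withdrawal trigger, but section 3.3 requires only an A1c and no pregnancy check is listed before either part, so an unrecognised pregnancy could go undetected

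*Combined protocol and SAP*

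**What the plan says.** The exclusion list in section 3.2 includes "Pregnancy or plan to become pregnant during the study period". The Study Summary and section 6.3 repeat the criterion, and none of the three places says how it is to be established. Section 3.4.1 makes it a continuing condition, since participants are withdrawn "if they develop any of the exclusion criteria after enrollment".

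On verification, section 3.3 is explicit: "The only laboratory testing necessary to meet inclusion/exclusion criteria will be a hemoglobin A1c done in the last month". Section 5 describes the screening visit, about 2 to 4 days before the first study day, as consent plus two checks: "the clinical history will be reviewed to be certain a volunteer meets the inclusion criteria and baseline hemoglobin A1c will be obtained". The screening row of the visit table has the same content in short form: qualification confirmed, consent, A1c.

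Women are enrolled. Section 5 says of the return interval: "This timing is selected to ensure that female participants are studied at the same phase of the menstrual cycle". Section 2.1 describes "two 2-day intervention visits separated by approximately 8 weeks", and the visit table's entry for the interval is "8 week wash out period Usual activities".

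**The concern.** Pregnancy status can change during the study, and early on the participant herself may not know it. A1c serves the glycemic inclusion criterion and carries no information about pregnancy. Section 3.3 does not merely leave the method open. It says that no other laboratory test is needed to apply the criteria, so a site that does no pregnancy test is following the protocol.

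What is at stake is participant safety. These are healthy volunteers in a proof-of-principle study (section 6.3), with no therapeutic benefit to set against the exposure. The protocol itself treats pregnancy as a reason not to undergo insulin-induced hypoglycemia and a blinded infusion of NAC or saline. An exclusion with no stated means of detecting the condition gives less protection than it appears to, and the withdrawal rule in section 3.4.1 then depends on the pregnancy coming to light some other way.

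**Working it through.** The plan gives no figure to reproduce. The check sets each place where pregnancy could be picked up beside what is listed there.

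| Stage | What the protocol lists | Pregnancy test listed |
|---|---|---|
| Eligibility rule (3.3) | A1c as the only necessary laboratory test | None |
| Screening (section 5, visit table) | Consent, clinical history, confirmation of qualification, A1c | None |
| Part 1 Day 1 baseline bloods (section 5) | Glucose, epinephrine, norepinephrine, cortisol, cysteine, glutathione | None |
| Washout (visit table) | Usual activities | None |
| Part 2 Day 1 (section 5, visit table) | Same procedures as Part 1, with the other treatment | None, and no eligibility re-check |

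No contraception requirement appears in any section.

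**Time without a listed check.** For women the return interval is 8 weeks, or 8 × 7 = 56 days. Adding the 2 to 4 days between screening and Part 1 gives roughly 58 to 60 days from the screening history to Part 2 Day 1.

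**Exposure if a pregnancy is missed.** The visit table has two clamps on Day 1 and one on Day 2, so 2 + 1 = 3 clamps per part. (Section 5 opens by calling the visits three-day, but its own description and table, and section 2.1, give two days.) Section 5 has each participant receive in Part 2 the treatment not given in Part 1, so NAC is given once.

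- Pregnancy present and unrecognised at entry, and still unrecognised at Part 2: up to 2 × 3 = 6 clamps and one NAC infusion.
- Pregnancy arising in the washout: up to 3 clamps, all in Part 2. NAC is given in that part only to women randomized to saline first; women randomized to NAC first receive saline.

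**Other routes to discovery.** Section 7.2 requires adverse-event questioning at each contact and examination as appropriate, but does not name pregnancy. Keeping women at the same menstrual phase gives staff a reason to ask about cycles, but no such question is written down. The screening history could identify a known or planned pregnancy, although section 5 ties it to the inclusion criteria and pregnancy is on the exclusion list.

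**The case against.** The best defense is that section 3.3 sets a minimum. Calling one test necessary does not forbid others, and the remaining exclusions, such as asthma, seizures and arrhythmias, are also applied by history. Participants can report a pregnancy at any time, section 3.4.1 applies throughout the study, and both cycle scheduling and adverse-event questioning give staff occasions to learn of one. Consent pages are also absent from the review copy, so a test described only there cannot be ruled out.

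Much of this stands. A reader might infer that every unrecognised pregnancy would get through, or that the withdrawal rule cannot work in Part 2. The documents support neither; the correct statement is that a pregnancy could go undetected. What does not stand is the comparison with the other exclusions. Those are mainly known diagnoses that a history can be expected to find, whereas an unrecognised pregnancy is by definition missing from the history. A test mentioned only in the consent form would conflict with section 3.3 and would still need reconciling.

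A reader might also see harm to the trial's answer through the loss of one of 15 planned pairs. Section 6.1 enrolls 18 to complete 15 and recruits more if needed, so a withdrawn participant is replaced. The loss is recruitment effort, not a fixed share of the data.

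**Conclusion.** The concern holds as a gap in participant safety and eligibility verification. Pregnancy is an exclusion and a withdrawal criterion, the only laboratory test said to be necessary cannot detect it, and no pregnancy test is listed at screening, in Part 1, in the washout or in Part 2. The possible consequence for an affected woman is up to three clamps in each part and, depending on sequence, her single NAC infusion.

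The textual finding is firm. The likelihood of the event is not known: the documents give neither the number of women of childbearing potential nor a conception rate, and women planning pregnancy are excluded. No expected count is offered, and with 18 participants it would probably be small.

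It would be tempting to read Part 2 as a second exposure to NAC for every returning woman. The crossover in section 5 rules that out. Nor does the point affect sample size, power or the primary model. The conclusion assumes that the consent form, not available here, does not supply the missing check.

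**What to change.** Reconcile section 3.3 with sections 3.2 and 3.4.1. Reword the sentence in 3.3 so that the required laboratory testing is *hemoglobin A1c and, for women of childbearing potential, a pregnancy test*. State that the result must be available before the Day 1 infusion of each part. Add the test to the Part 1 Day 1 and Part 2 Day 1 rows of the visit table, and bring the consent form into line if it says something different.

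A urine point-of-care test would suit the schedule. Participants arrive by 7 am and the infusion starts between 8 and 9 am, so a laboratory assay on the baseline blood might not report in time. A further test at screening, only 2 to 4 days before Part 1, is not needed to close the gap.

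The cost is about two inexpensive tests per woman of childbearing potential and a short amendment. With the planned 18 participants that is at most 18 × 2 = 36 tests, even if all were such women. No extra visit, staff or invasive procedure is required, and the dosing, clamps, sample size and analysis are unchanged.

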3.4 Early Withdrawal of Subjects

3.4.1 When and How to Withdraw Subjects

Subjects will be withdrawn at any point during the study if they remove their consent or if they develop any of the exclusion criteria after enrollment. In addition, any subjects who experience the symptoms of an allergic reaction to the NAC severe enough that the infusion is stopped early will be withdrawn from the study at the time the infusion is stopped (before unblinding that participant's treatment assignment). Procedures for withdrawal include collecting the necessary information to provide them with the compensation due them for the time they devoted to the study. At the end of the study, after treatment assignments are unblinded, a letter will be sent to the any subject withdrawn because of symptoms of an allergic reaction to NAC informing them of the treatment they were given. If they had been given NAC, we will instruct them to share the letter with their personal physician so the allergy could be noted in the clinical record.

3.4.2 Data Collection and Follow-up for Withdrawn Subjects

Data will be collected per the protocol up until the point the subject is withdrawn from the study. No additional data will be collected from subjects after their withdrawal unless they were withdrawn due to early stopping of the infusion. For such participants, a follow-up phone call within 1-2 days will ascertain their status and if hospitalized we will request consent to access hospitalization records. NAC is already used in clinical practice for other indications and it does not have an effect on survival.

CONFIDENTIAL

4 Study Drug

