7.1 Definitions

Adverse Event

An **adverse event** (AE) is any symptom, sign, illness or experience that develops or worsens in severity during the course of the study. Intercurrent illnesses or injuries will be regarded as adverse events. Abnormal results of diagnostic procedures are considered to be adverse events if the abnormality:

- results in study withdrawal
- is associated with a serious adverse event
- is associated with clinical signs or symptoms
- leads to additional treatment or to further diagnostic tests
- is considered by the investigator to be of clinical significance.

Serious Adverse Event

Adverse events are classified as serious or non-serious. A **serious adverse event** is any AE that is:

CONFIDENTIAL

- fatal
- life-threatening
- requires or prolongs a hospital stay
- results in persistent or significant disability or incapacity
- a congenital anomaly or birth defect
- an important medical event.

Important medical events are those that may not be immediately life threatening, but are clearly of major clinical significance. They may jeopardize the subject, and may require intervention to prevent one of the other serious outcomes noted above. For example, drug overdose or abuse, a seizure that did not result in in-patient hospitalization, or intensive treatment of bronchospasm in an emergency department would typically be considered serious.

All adverse events that do not meet any of the criteria for serious should be regarded as ***non-serious adverse events***.

Adverse Event Reporting Period

The study period during which adverse events must be reported is normally defined as the period from the initiation of any study procedures to the end of the study treatment follow-up. For this study, the study treatment follow-up is defined as 30 days following the last administration of study treatment.

Preexisting Condition

A preexisting condition is one that is present at the start of the study. A preexisting condition will be recorded as an adverse event if the frequency, intensity, or the character of the condition worsens during the study period.

General Physical Examination Findings

At screening, any clinically significant abnormality will be recorded as a preexisting condition. At the end of the study, any new clinically significant findings/abnormalities that meet the definition of an adverse event will also be recorded and documented as an adverse event.

Post-study Adverse Event

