7.2 Recording of Adverse Events

At each contact with the subject, the investigator must seek information on adverse events by specific questioning and, as appropriate, by examination. Information on all adverse events will be recorded immediately in the source document, and also in the appropriate adverse event module of the case report form (CRF). All clearly related signs, symptoms, and abnormal diagnostic procedures results will be recorded in the source document, though should be grouped under one diagnosis.

All adverse events occurring during the study period must be recorded. The clinical course of each event will be followed until resolution, stabilization, or until it has been determined that the study treatment or participation is not the cause. Serious adverse events that are still ongoing at the end of the study period must be followed up to determine the final outcome. Any serious adverse event that occurs after the study period and is considered to be possibly related to the study treatment or study participation should be recorded and reported immediately.

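### Section 3.4.2 ends data collection at withdrawal, which conflicts with the adverse event follow-up that sections 7.1 to 7.3.1 require for all participants, including those withdrawn because of a serious event

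*Combined protocol and SAP*

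**What the plan says.** Section 3.4.1 sets the withdrawal triggers. Besides withdrawn consent and an infusion stopped early for allergic symptoms, a participant is withdrawn "if they develop any of the exclusion criteria after enrollment". The list in section 3.2 includes "History of diabetes, hyperglycemia, stroke, seizures, arrhythmias, active cardiac disease".

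Section 3.4.2 keeps the data gathered up to withdrawal and then closes collection: "No additional data will be collected from subjects after their withdrawal unless they were withdrawn due to early stopping of the infusion". For the excepted group it provides this: "For such participants, a follow-up phone call within 1-2 days will ascertain their status". If such a participant is hospitalized, consent to see the hospital records is requested.

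Section 7 sets the safety duties. In 7.1 the adverse event reporting period runs to the end of follow-up, and "the study treatment follow-up is defined as 30 days following the last administration of study treatment". Section 7.1 also has the investigator follow unresolved events until they resolve, are otherwise explained, or the participant is lost to follow-up. Section 7.2 adds: "Serious adverse events that are still ongoing at the end of the study period must be followed up to determine the final outcome". Section 7.3.1 requires a serious event to reach the monitoring board within 24 hours, a written narrative within the next 48 hours, and prompt reporting of significant new information.

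**The concern.** Because 3.4.1 reuses the exclusion list as a withdrawal trigger, several conditions that would count as serious adverse events also end a participant's data collection under 3.4.2. Section 7.1 itself gives a seizure without admission as a typical serious event. Read literally, 3.4.2 stops safety follow-up because the event happened.

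Section 3.4.2 supports its limited follow-up by noting that NAC is in clinical use and does not affect survival. That says nothing about harm from the clamps. Each part of the study includes three of them, and the day 2 clamp steps down to a 45 mg/dl target.

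What is at stake is the safety record of a small Phase I/II study in healthy volunteers. The board reviews adverse events at least monthly. If 3.4.2 were followed, it might never learn how a non-allergic serious event ended.

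**Working it through.** The plan states no figure to reproduce. The check sets the sections side by side and then subtracts the follow-up that 3.4.2 allows from the window that 7.1 requires.

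**Step 1. The chain of rules.** A participant has a seizure during the day 2 clamp. Under 3.2 a history of seizures is an exclusion criterion. Under 3.4.1 the participant is withdrawn. No study infusion is given on day 2, so the exception in 3.4.2 cannot apply and collection ends. Under 7.1, 7.2 and 7.3.1 the same event must be described in a narrative, updated, and followed to its outcome. Staff cannot do both.

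**Step 2. Does Section 7 yield to 3.4.2, or the reverse?** Sections 7.1, 7.2 and 7.3.1 contain no exception for withdrawn participants. Section 3.4.2 does not refer to Section 7. No other section ranks them. Section 8.1 even asks staff to seek permission for at least vital status from participants who revoke authorization. Taken literally, 3.4.2 therefore does less for a consenting participant withdrawn after a stroke than 8.1 does for one who revokes authorization.

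**Step 3. Size of the gap.** Inputs: a 30-day window after the last study treatment (7.1); no contact after withdrawal on an exclusion criterion, and one call at 1-2 days after early stopping of the infusion (3.4.2); infusion on day 1 only (4.2); about 8 weeks, or 8 × 7 = 56 days, between parts (2.1, 5).

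For a participant withdrawn on an exclusion criterion *d* days after the last infusion, the part of the window lost is max(0, 30 − *d*).

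| Situation | Arithmetic | Window not covered |
|---|---|---|
| Infusion day, after the infusion has ended | 30 − 0 | up to 30 days |
| Day 2 clamp | 30 − 1 | 29 days |
| Washout, day 14 (illustrative) | 30 − 14 | 16 days |
| Washout, day 30 to about day 56 | max(0, 30 − *d*) | 0 days |
| Infusion stopped early, only contact at 1-2 days | 30 − 1, 30 − 2 | 28 to 29 days |

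The duty to follow unresolved events has no fixed end. For an event still open, that duty also conflicts with 3.4.2 after day 30, and the table does not count this.

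**The case against.** The strongest reply is that Section 7 already orders the follow-up. The triggering event is recorded, because 3.4.2 keeps data up to withdrawal. The board hears of a serious event within 24 hours, and ongoing serious events must be pursued. A conscientious investigator would follow Section 7. This stands to the extent that lost outcomes are a risk and not a certainty. It does not remove the conflict, since 3.4.2 is explicit and is the section that staff would consult on a withdrawal.

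A second reply is that a seizure during the day 1 infusion might come under the exception, whose wording does not mention allergy. Sections 3.4.1 and 7.5 tie early stopping to allergic symptoms, so the reading is unclear. The example is clean only where no infusion is running, as on day 2 or in the washout.

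Three stronger readings might be inferred, and the documents do not support them:

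- *That up to one in six participants is affected*, from 18 − 15 = 3 and 3/18 = 16.7%. Those 3 are a general allowance for incomplete data sets from any cause, and section 6.1 permits further recruitment. The figure neither estimates nor bounds these events.
- *That uneventful participants have complete follow-up*, which would make the contrast stark. The visit table in Section 5 ends at Part 2 day 2 and schedules no 30-day contact for anyone. Afterwards participants are only told to report events they think may be related.
- *That 3.4.2 is what prevents a birth defect from being learned*, since pregnancy is an exclusion criterion and birth defect a serious event category. Such an outcome would ordinarily emerge well beyond 30 days, and Section 7 sets up no pregnancy follow-up. Aligning 3.4.2 with Section 7 would not fill that gap.

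**Conclusion.** The contradiction is real and lies in current text. If 3.4.2 is followed, safety follow-up of a participant withdrawn on an exclusion criterion could be shortened by up to 30 days of the required window: 29 days for an event on day 2, falling to none by day 30 of the washout. Where the infusion exception applies, the one specified call leaves 28 to 29 days uncovered.

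These figures rest on two assumptions: that staff act on 3.4.2 and not on Section 7, and that no contact beyond those named in 3.4.2 takes place. The number of participants affected cannot be estimated, because the documents give no rate for stroke, seizure, arrhythmia or cardiac disease in this setting. The point concerns safety data only. The primary endpoint, its analysis and the sample size are not touched. It should be corrected because the conflict affects serious events and is cheap to remove.

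**What to change.** Reconcile 3.4.2 with Section 7. Limit the sentence in 3.4.2 to study procedures and efficacy samples. Then state that adverse event collection and follow-up under 7.1 to 7.3 continue for every withdrawn participant who received any study infusion or underwent any clamp, unless that participant withdraws consent to follow-up. Keep the call at 1-2 days as an additional contact after an early-stopped infusion.

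This leaves the withdrawal triggers, the infusion, the clamps and the stopping boundary as they are. It costs one amended sentence and some added contact with the few withdrawn participants. The contact is a small real burden, since 7.1 sets a reporting period but does not itself schedule a call.
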